8.2 Pegylated Liposomal Doxorubicin (PLD) Dose Delays and Adjustments

If a toxicity occurs that requires toxicity management in accordance with Sections 8.2, 8.3, or 8.4, and the toxicity causing drug can be clearly identified, then the respective guideline should be followed. If the toxicity causing drug cannot be identified, then the more conservative guideline should be followed.

Please refer to the package insert/product information for pegylated liposomal doxorubicin (PLD) for current instructions on dose delays and adjustments.

Subjects should be carefully monitored for toxicity. Adverse reactions, such as HFS, hematologic toxicities, and stomatitis may be managed by dose delays and adjustments. Following the first appearance of a Grade 2 or higher adverse reactions, the dosing should be adjusted or delayed as described in the following tables. Once the dose has been reduced, it should not be increased at a later time.

In the event of a delay in PLD dosing due to drug-related toxicity, doses of MEDI4736 and motolimod should also be delayed, as per Section 3.1.8.

As the standard of care agent, PLD is administered every 28 days. Every effort should be made to adhere to this schedule. Delays due to motolimod and/or MEDI4736 should not delay or shift the timing of PLD dosing.

8.2.1 Hematological Toxicity

Grade	ANC	Platelets	Modification
1	1,500 – 1,900	75,000 – 150,000	Resume treatment with no dose reduction.
2	1,000 – <1,500	50,000 – <75,000	Wait until ANC \geq 1,500 and platelets \geq 75,000; redose with no dose reduction.
3	500 – 999	25,000 – <50,000	Wait until ANC \geq 1,500 and platelets \geq 75,000; redose with no dose reduction.
4	<500	<25,000	Wait until ANC \geq 1,500 and platelets \geq 75,000; redose at 25% dose reduction or continue full dose with cytokine support.

8.2.2 Hand Foot Syndrome (HFS)

HFS Toxicity Grade	Dose Adjustment
1 (mild erythema, swelling, or desquamation not interfering with daily activities)	Redose unless subject has experienced previous Grade 3 or 4 HFS. If so, delay up to 2 weeks and decrease dose by 25%. Return to original dose interval.
2 (erythema, desquamation, or swelling interfering with, but not precluding normal physical activities; small blisters or)	Delay dosing up to 2 weeks or until resolved to Grade 0-1. If after 2 weeks there is no resolution, PLD should be discontinued. If resolved to Grade 0-1 within 2 weeks, and there are no prior Grade 3-4 HFS, continue treatment at previous dose and return to original dose interval.

CONFIDENTIAL

ulcerations less than 2 cm in diameter)	If subject experienced previous Grade 3-4 toxicity, continue treatment with a 25% dose reduction and return to original dose interval.
3 (blistering, ulceration, or swelling interfering with walking or normal daily activities; cannot wear regular clothing)	Delay dosing up to 2 weeks or until resolved to Grade 0-1. Decrease dose by 25% and return to original dose interval. If after 2 weeks there is no resolution, PLD should be discontinued.
4 (diffuse or local process causing infectious complications, or a bedridden state or hospitalization)	Delay dosing up to 2 weeks or until resolved to Grade 0-1. Decrease dose by 25% and return to original dose interval. If after 2 weeks there is no resolution, PLD should be discontinued.

8.2.3 Stomatitis

Stomatitis Toxicity Grade	Dose Adjustment
1 (painless ulcers, erythema, or mild soreness)	Redose unless subject experienced previous Grade 3 or 4 toxicity. If so, delay up to 2 weeks and decrease dose by 25%. Return to original dose interval.
2 (painful erythema, edema, or ulcers, but can eat)	Delay dosing up to 2 weeks or until resolved to Grade 0-1. If after 2 weeks there is no resolution, PLD should be discontinued. If resolved to Grade 0-1 within 2 weeks and there was no prior Grade 3-4 stomatitis, continue treatment at previous dose and return to original dose interval. If subject experienced previous Grade 3-4 toxicity, continue treatment with a 25% dose reduction and return to original dose interval.
3 (painful erythema, edema, or ulcers, and cannot eat)	Delay dosing up to 2 weeks or until resolved to Grade 0-1. Decrease dose by 25% and return to original dose interval. If after 2 weeks there is no resolution, PLD should be discontinued.
4 (requires parenteral or enteral support)	Delay dosing up to 2 weeks or until resolved to Grade 0-1. Decrease dose by 25% and return to PLD original dose interval. If after 2 weeks there is no resolution, PLD should be discontinued.

8.2.4 Subjects with Impaired Hepatic Function

Limited clinical experience exists in treating subjects with hepatic impairment with PLD. Based on experience with doxorubicin HCl, it is recommended that the PLD dosage be reduced if the bilirubin is elevated as follows: serum bilirubin 1.2 to 3.0 mg/dL - give 50% normal dose; serum bilirubin >3 mg/dL - give 25% normal dose, or proceed according to institutional standards.

CONFIDENTIAL

8.3 Motolimod Toxicity Management and Dose Adjustments

PER Amendment 2, motolimod dosing will be discontinued for all subjects.

If a toxicity occurs that requires toxicity management in accordance with Sections 8.2, 8.3, or 8.4, and the toxicity causing drug can be clearly identified, then the respective guideline should be followed. If the toxicity causing drug cannot be identified, then the more conservative guideline should be followed.

8.3.1 Management of Injection Site Reactions

Acute symptoms of injection site reactions typically resolve within 48 hours of injection, but more persistent reactions are not unexpected. Grade 2 and 3 reactions may include a painful, raised, fluid-filled blister that mimics a sterile abscess. Injection site reactions do not typically warrant antibiotic intervention as they have been found to be sterile. A culture of the fluid can be obtained—using sterile technique—if infection is strongly suspected (i.e., associated with fever persisting more than 24 hours after injection).

Ice and acetaminophen should be administered prophylactically. Symptomatic treatment with ice, acetaminophen and narcotics is acceptable. Due to their potentially suppressive effects, the use of NSAIDs within 24 hours of dosing with motolimod should be avoided, if clinically feasible.

8.3.2 Management of Systemic Toxicities

The most common systemic drug-related adverse events—Grade 1 or 2 chills, flu-like symptoms and fever—typically resolve in < 48 hours and do not require dose reductions or a delay in the dosing regimen. Less commonly, dosing with motolimod may result in cytokine release syndrome (CRS), which is most likely to be grade 1 or 2, but more severe reactions have been reported.

CRS is a symptom complex and is characterized by systemic symptoms which may include fever, nausea, chills, tachycardia, hypotension, dyspnea, asthenia, headache, and rash. Motolimod directly targets TLR8, which is expressed on immune cells. CRS may result from the release of cytokines from the activated immune cells, or from ‘downstream’ events that can be associated with cytokine production. Symptoms of CRS may be acute or delayed by several hours after dosing with motolimod.

Treatment of systemic drug-related events should be consistent with the severity of the reaction as well as institutional standards and may include: acetaminophen, H1- and H2-receptor antagonists, narcotics, IV fluids for volume expansion, and supplemental oxygen. Due to their potentially immunosuppressive effect, administration of NSAIDs and systemic steroids (e.g., dexamethasone) should be avoided if other means of treatment are available and medically appropriate.

In most cases the CRS will be Grade 1 or 2. However, a severe, life-threatening reaction resulting from a substantial release of cytokines is possible. Severe CRS is a medical emergency and urgent intervention must be taken to prevent life-threatening complications. This may include administration of sympathomimetic amines for pressor support and/or hospitalization for acute monitoring and intervention.

CONFIDENTIAL

8.3.3 Motolimod Dose Modifications due to Toxicities

Motolimod will be dosed as defined in Section 3.1.7. Any dose reductions that become necessary due to the toxicities outlined below, should be done in steps of 1 level of 0.5 mg/m², down to a minimum dose of 1.5 mg/m². If 1.5 mg/m² is not tolerated, motolimod should be discontinued. Delays in motolimod dosing should not delay or shift the timing of other treatment agents. In the event of Grade 3 or 4 toxicities attributed to motolimod, subsequent doses should be delayed until recovery to ≤ Grade 1.

8.3.3.1 Cytokine Release Syndrome

Grade 1	Dose reduction not required; consider prophylactic precautions—including volume expansion and treatment with oral or IV antihistamines—with next dose.
Grade 2	Reduce dose by 1 level at investigator’s discretion; consider prophylactic precautions—including volume expansion and treatment with oral or IV antihistamines—with next dose.
Grade 3-4	Reduce dose by 1 level; use prophylactic precautions with next dose.

8.3.3.2 Injection Site Reaction

Grade 1	Dose reduction not required; consider administering subsequent injections at distal anatomic site(s).
Grade 2	Delay dosing for up to 2 weeks if needed; administer subsequent injections at distal anatomic site(s) until resolved to ≤ grade 1.
	Reduce dose by 1 level if > 2 weeks delay or > 2 delays are required with consecutive injections.
Grade 3-4	Reduce dose by 1 level; delay dosing until resolved to ≤ grade 1.

8.3.3.3 Non-Hematologic Drug-Related AEs

Grade 1–2	Dose reduction not required; manage per institutional standards.
Grade 3-4	Reduce dose by 1 level.

8.3.3.4 Hematologic Drug-Related AEs

Grade 1–3	Dose reduction not required; manage per institutional standards.
Grade 4	Reduce dose by 1 level.

8.4 MEDI4736 Toxicity Management and Dose Adjustments

If a toxicity occurs that requires toxicity management in accordance with Sections 8.2, 8.3, or 8.4, and the toxicity causing drug can be clearly identified, then the respective guideline should be followed. If the toxicity causing drug cannot be identified, then the more conservative guideline should be followed.

8.4.1 Management of MEDI4736-related Toxicities

Based on the mechanism of action of MEDI4736 leading to T-cell activation and proliferation, Immune-related Adverse Events (irAE) may be observed during the conduct of this study. IrAEs are defined as AEs of immune nature (i.e., inflammatory) in the absence of a clear alternative etiology. Subjects should be monitored for signs and symptoms of irAEs.

Potential irAEs with MEDI4736 are expected to be similar to those seen with other immune checkpoint inhibitors, and may include immune-mediated enterocolitis, pneumonitis, dermatitis, hepatotoxicity or hepatitis, endocrinopathy, neurotoxicity and uveitis.

It is recommended that management of irAEs follow the Medimmune Guideline for Toxicity Management for MEDI4736 [**“Medimmune’s Dosing Modification and Toxicity Management Guidelines for Immune-mediated, Infusion Related, and Non Immune-mediated Reactions (MEDI4736 Monotherapy or Combination therapy with Tremelimumab or Tremelimumab monotherapy)”**] and the current MEDI4736 Investigator’s Brochure.

In general, the following is recommended:

1. Subjects should be evaluated to identify any alternative etiology.
2. In the absence of clear alternative etiology, all events of an inflammatory nature should be considered to be immune-related.
3. Symptomatic and topical therapy should be considered for low-grade events.
4. Systemic corticosteroids should be considered for a persistent low-grade event or for a severe event.
5. More potent immunosuppressive therapies should be considered for events not responding to systemic steroids (e.g., infliximab, mycophenolate, etc.).

8.4.2 MEDI4736 Dose Modifications due to Toxicities

MEDI4736 may have to be modified or discontinued due to toxicities. Dose modifications will not be required for AEs that are clearly not attributed to MEDI4736 (such as an accident) or for laboratory abnormalities that are not deemed to be clinically significant. Delays in MEDI4736 dosing should not delay or shift the timing of other study drugs.

Note: If MEDI4736 dosing is held temporarily until resolution of the event as per instructions below, treatment should resume at the next scheduled treatment date (and not at the date of resolution).

8.4.2.1 Immune-related Adverse Events (irAEs)

Immune-related adverse events are defined as AEs of immune nature (i.e., inflammatory) in the absence of a clear alternative etiology. Maximum supportive care, including immunosuppressive medications, such as high dose steroids is allowed to induce resolution of the event. **However, infliximab should not be used for management of immune-related hepatitis.**

In addition to the criteria for permanent discontinuation of MEDI4736 depicted below, **permanently discontinue MEDI4736** also for:

- Any Grade rash with bullous skin formations.
- Inability to reduce corticosteroid to a dose of ≤ 10 mg of prednisone per day (or equivalent) within 12 weeks after last dose of study drug/regimen.
- Recurrence of a previously experienced Grade 3 treatment-related AE following resumption of dosing.

Grade 1	
 • In general, no dose modification required. • For pneumonitis/interstitial lung disease and myocarditis, consider holding MEDI4736 dosing as clinically appropriate and during diagnostic work-up for other etiologies.
Grade 2	
 • In general, hold MEDI4736 until resolution to \leq Grade 1 and after the end of any steroid taper, and discontinue MEDI4736 permanently if such resolution does not occur within 60 days (30 days for neurotoxicities). Criteria for temporary hold or permanent discontinuation of MEDI4736 may differ by event as detailed below. • For pneumonitis/interstitial lung disease and myocarditis, the decision to reinitiate MEDI4736 upon resolution shall be based upon treating physician's clinical judgment (as long as the event does not meet DLT criteria). • For peripheral neuromotor syndromes, such as Guillain-Barre and Myasthenia Gravis, follow general instructions above, but always discontinue MEDI4736 permanently if there are signs of respiratory insufficiency or autonomic instability. • For endocrinopathies, other than isolated hypothyroidism, follow general instructions above, but subjects may be retreated if the endocrinopathy is controlled and the subject is clinically stable while requiring steroid doses of ≤ 10 mg/day prednisone equivalent. • For isolated hypothyroidism managed with hormone replacement therapy, and for sensory neuropathy/neuropathic pain, holding MEDI4736 is at the discretion of the Investigator. • For elevated creatinine or rash, MEDI4736 should be held until resolution to \leq Grade 1 or baseline. • For vitiligo, no dose modification required.

Grade 3	
 • In general, hold MEDI4736 until resolution to \leq Grade 1, and after the end of any steroid taper, and discontinue MEDI4736 permanently if such resolution does not occur within 60 days (30 days for neurotoxicities and rash). Criteria for permanent discontinuation of MEDI4736 may differ by event as detailed below. • For peripheral neuromotor syndromes (such as Guillain-Barre and Myasthenia Gravis), apply respective Grade 2 rules. • For endocrinopathies, follow Grade 2 instructions above. • For pneumonitis/interstitial lung disease, diarrhea/enterocolitis, myocarditis and elevated serum creatinine (e.g., nephritis or renal dysfunction), always discontinue MEDI4736 permanently. • For asymptomatic increases of amylase or lipase levels, hold MEDI4736, and if complete work up shows no evidence of pancreatitis, MEDI4736 may be continued. • For hepatitis, discontinue MEDI4736 permanently for (1) transaminases or bilirubin not resolving to \leq Grade 1 or baseline within 14 days, (2) transaminases $> 8 \times$ upper limit of normal (ULN) or bilirubin $> 5 \times$ ULN, or (3) any case meeting Hy's law criteria (as defined in FDA Guidance Document "Drug-Induced Liver Injury"). • For rash, MEDI4736 should be held until resolution to \leq Grade 1 or baseline.
Grade 4	
 • In general, discontinue MEDI4736 permanently. • For endocrinopathies, follow Grade 2 instructions above. • For asymptomatic increases of amylase or lipase levels, hold MEDI4736, and if complete work up shows no evidence of pancreatitis, MEDI4736 may be continued.

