3.1.9 DLT and MTD

PER Amendment 2, motolimod dosing will be discontinued for all subjects.

DLTs will be observed over a period of the first cycle including the pre-dose assessment for Cycle 2, defined as the “DLT Evaluation Period”. The decisions for dose escalations, de-escalations and MTD, as described in Section 3.1.7, will primarily be based on the number of subjects with DLTs occurring during the DLT Evaluation Period. DLTs occurring outside the DLT Evaluation Period will also be evaluated and may impact such decisions.

DLTs are defined as any adverse events that are possibly, probably, or definitely related to the administration of MEDI4736, motolimod or PLD, and fulfill any of the following criteria:

1. Any Grade \geq 3 colitis, pneumonitis, neurological event, or uveitis.
2. Any Grade 2 pneumonitis, neurological event, or uveitis with the following exception:
 - Grade 2 pneumonitis, neurological event, or uveitis that downgrades to Grade \leq 1 within 3 days after onset, whereby maximal supportive care, including systemic corticosteroids, is permitted.
3. Any *other* Grade \geq 3 toxicity, with the following exceptions:
 - Grade \geq 3 PLD-related toxicities, manageable according to the dose modification instructions in the package insert/product information (see Section 8.2.)
 - Grade 3 irAEs (see definition below) that downgrade to Grade \leq 2 within 3 days, or to Grade \leq 1 or baseline within 14 days after onset, whereby maximal supportive care, including systemic corticosteroids, is permitted.
 - Grade 3 endocrinopathy that becomes asymptomatic when managed with or without systemic corticosteroid therapy and/or hormone replacement therapy.
 - Grade 3 inflammatory reaction attributed to a local antitumor response (e.g., inflammatory reaction at sites of metastatic disease, lymph nodes, etc.).
 - Grade 3 fatigue for \leq 7 days.
 - Grade 3 infusion-related reaction (first occurrence and in the absence of steroid prophylaxis) that resolves within 6 hours with appropriate clinical management.
 - Liver transaminase elevation \leq 8 times ULN that downgrades to Grade \leq 2 (\leq 5 times ULN) within 7 days after onset, whereby maximal supportive care, including systemic corticosteroids, is permitted.
 - Total bilirubin \leq 5 times ULN that downgrades to Grade \leq 2 (\leq 3 times ULN) within 7 days after onset, whereby maximal supportive care, including systemic corticosteroids, is permitted.

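### The permanent MEDI4736 stop for Hy's law cases is written only in the Grade 3 row of Protocol 8.4.2.1, so a case graded 2 could be read as eligible for rechallenge

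*Protocol*

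**What the plan says.** Protocol 8.4.2.1 has two layers. Above the grade table is a short list of permanent stops that do not depend on the row. It has three items: bullous rash ("Any Grade rash with bullous skin formations"), failure to taper corticosteroids, and recurrence of a related Grade 3 event after restarting. None concerns the liver.

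Below it, each grade has its own row.

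- **Grade 2.** The default is to hold until the event is down to at most "Grade 1 and after the end of any steroid taper, and discontinue MEDI4736 permanently if such resolution does not occur within 60 days". The row then says: "Criteria for temporary hold or permanent discontinuation of MEDI4736 may differ by event as detailed below". The bullets that follow cover lung and heart, neuromotor, endocrine, sensory, creatinine, rash and vitiligo events. There is no hepatitis bullet.
- **Grade 3.** A hepatitis bullet gives three grounds for a permanent stop. The first begins "transaminases or bilirubin not resolving to" and sets a recovery limit, the second sets upper limits on the values, and the third is "any case meeting Hy's law criteria". Hy's law is defined there only by citing an FDA guidance.

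For held doses in general, 8.4.2 adds that "treatment should resume at the next scheduled treatment date (and not at the date of resolution".

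**The concern.** The words *any case* sound independent of grade, but their position ties them to Grade 3. An investigator managing a liver event graded 2 looks in the Grade 2 row and finds only the general hold. If a Hy's law case can be graded 2, the table supports two answers: stop for good, or hold and restart after recovery.

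At stake is the safety of individual subjects. The same combined signal in transaminases and bilirubin could end treatment at one site and allow rechallenge at another, depending on how the table is read.

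**Working it through.** The plan gives no figure to reproduce. The check asks whether a Hy's law case can sit in the Grade 2 row, and whether any other rule then forces a permanent stop.

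**1. Can such a case be graded 2?**

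- Grade 2 ceilings come from the DLT exceptions in Protocol 3.1.9, which equate Grade 2 or lower with transaminases up to 5 x ULN ("5 times ULN) within 7 days after onset") and bilirubin up to 3 x ULN ("3 times ULN) within 7 days after onset").
- The combined threshold comes from Protocol 7.1.8, which defines hepatic function abnormality as ALT or AST above 3 x ULN with concurrent bilirubin above 2 x ULN. The same paragraph has cases at 3 x or 2 x evaluated against Hy's law for SAE reporting.

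Let Hy's law start at ALT/AST above a x ULN and bilirubin above b x ULN, and grade the event by its analytes. The overlap with Grade 2 is then ALT/AST in (a, 5] and bilirubin in (b, 3]. It exists only if a < 5 and b < 3.

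| Assumed start (a, b) | ALT/AST range, x ULN | Bilirubin range, x ULN | Overlap |
|---|---|---|---|
| (3, 2), the values in 7.1.8 | above 3 to 5 | above 2 to 3 | yes |
| (4, 2) | above 4 to 5 | above 2 to 3 | yes, narrower |
| (5, 2) | none | above 2 to 3 | no |
| (3, 3) | above 3 to 5 | none | no |

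With the 7.1.8 values, ALT at 4 x ULN with bilirubin at 2.5 x ULN qualifies, since 3 < 4 ≤ 5 and 2 < 2.5 ≤ 3.

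**2. Which reading does the table favour?**

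- For an override of grade: the words *any case*, and the fact that the Grade 2 hold is only a general rule that yields to event-specific criteria.
- For a row-bound rule: in both the Grade 2 and Grade 3 rows, the pointer to event-specific criteria is followed by that row's own bullets. Where the authors wanted a rule to cross rows they said so, as with endocrinopathies and neuromotor syndromes in the Grade 3 row, which are sent back to Grade 2. Where they wanted a stop at every grade they put it in the upper list, as with bullous rash.

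Neither reading can be excluded.

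**3. Does another rule force a permanent stop at Grade 2?**

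- 7.1.2.3 requires immediate interruption when no definitive diagnosis is reached, 24-hour reporting, and evaluation by the sponsor and manufacturer. It does not require discontinuation.
- 7.1.8 makes a case that meets Hy's law an SAE, and 7.1.6 has the Medical Monitor evaluate it. These are reporting and review steps.
- 3.1.9 makes only pneumonitis, neurological events and uveitis DLTs at Grade 2, unless they improve quickly. Other events below Grade 3 can be designated DLTs after consultation, and treatment after a DLT may continue by agreement.
- 8.4 says to follow the more conservative guideline when the causative drug is unknown. That concerns which drug is responsible, not which grade row applies.
- 8.4.2.3, for events that are not immune-related, also gives a 60-day hold at Grade 2 with no Hy's law item.
- 8.4.1 only recommends the manufacturer's toxicity guideline.

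So under the row-bound reading no mandatory permanent stop applies.

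**The case against.** Four points can be made on the other side.

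**The definition is outside the documents.** Section 8.4.2.1 takes Hy's law from a guidance that is only cited, and the 3 x and 2 x pair in 7.1.8 defines a separately named abnormality. This stands as a limit, and the table above shows the overlap vanishing if the true start is high enough. It does not remove the point, because 7.1.8 itself starts the Hy's law evaluation from these values.

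**The wording already covers Grade 2.** *Any case* may well be meant to do so. If so, moving the words changes nothing in substance and removes the doubt.

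**The placement may come from the manufacturer.** The version history says that 8.4.2 was updated to the manufacturer's guideline, whose text is not available here. This stands. It bears on the origin of the wording and on the cost of changing it.

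**Other controls are tight.** With a 3 x and 2 x start, every case in the overlap is also a hepatic function abnormality under 7.1.2.3. That section leaves continued dosing to the investigator's judgment only when a diagnosis unrelated to the investigational product has been established. Such a case has an alternative cause, so by definition it is not an immune-related event. The remaining cases are interrupted, reported and evaluated. This also stands, and it limits the harm to a considered decision to restart.

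A reader might infer more: that subjects would be dosed during the 60-day window, that the protocol compels a restart, or that a rechallenge could go unnoticed. The documents do not support these. Doses in that window are held. The sentence in 8.4.2 on resuming fixes when a restart happens, and the Grade 2 rule permits a restart without ordering one. Interruption, expedited reporting and review make an unnoticed rechallenge unlikely.

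**Conclusion.** The ambiguity is real and narrow. Under the row-bound reading, a combined elevation with ALT/AST above 3 and up to 5 x ULN and bilirubin above 2 and up to 3 x ULN follows the Grade 2 hold, and MEDI4736 may restart after recovery and any steroid taper. This rests on two assumptions that the documents do not settle: that Hy's law begins near the 7.1.8 values, and that the event is graded by its analytes. If it begins at or above 5 x or 3 x ULN, or if the combined event is graded 3 or higher on clinical grounds, there is no gap.

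The exposure is a deliberate rechallenge after sponsor and manufacturer review. How often it could arise among the 6 to 53 evaluable subjects cannot be derived and may be zero. Sample size, error rates and trial results are unaffected. It would be wrong to conclude that the protocol lacks liver safeguards: it has several, but none is a mandatory permanent stop at Grade 2. This is a cheap improvement to safety wording.

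**What to change.** Move the Hy's law criterion from the Grade 3 hepatitis bullet to the permanent-discontinuation list at the top of 8.4.2.1, beside the bullous rash item. Alternatively, leave it in place and add that it applies regardless of grade. Cross-refer to it from 7.1.2.3, so that the section that triggers interruption also points to the stop.

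The cost is one criterion moved or one phrase added, plus one cross-reference, with no new visits or assessments. There are two downsides. A rare Hy's law case graded 2 loses the option of rechallenge. The text may also differ from the manufacturer's guideline, so the two should be compared before the change is made.
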